8 SAFETY EVALUATION

8.1 Adverse Events (AEs)

8.1.1 Definition of adverse event

An adverse event (AE) refers to any untoward medical occurrence in a study subject administered a medicinal product and which does not necessarily have a causal relationship with this treatment. For the specific period of AE collection in this study, please refer to Section 8.3. AEs include the following:

- 1) Worsening of pre-existing (prior to entering clinical study) medical conditions/diseases (including worsening symptoms, signs, or laboratory abnormalities);
- 2) Any new AEs: Any new adverse medical conditions (including symptoms, signs, and newly diagnosed diseases);
- 3) Clinically significant abnormal laboratory findings.

The investigator should record any AEs that have occurred in detail, including the description of the AEs and all relevant symptoms, time of occurrence, severity, causality with the study drugs, duration, measures taken, and final results and outcomes.

8.1.2 Criteria for severity assessment of adverse events

The severity of AEs will be determined using NCI-CTCAE v4.03. The following criteria can be used as references if an unlisted AE occurs:

Grade 1: mild; asymptomatic or mild symptoms; clinical or diagnostic observations only; treatment not indicated.

Grade 2: moderate; minimal, local, or non-invasive intervention indicated; limiting age-appropriate instrumental activities of daily living (e.g., cooking, shopping, using the telephone, counting money, etc.);

Grade 3: severe or medically significant but not immediately life-threatening; hospitalization or prolongation of hospitalization indicated; disabling; limiting self-care activities of daily living. Self-care ADL: Refer to bathing, dressing and undressing, feeding self, using the toilet, taking medications, and not bedridden.

Grade 4: life-threatening consequences; urgent intervention indicated.

Grade 5: death related to AE.

8.1.3 Criteria for the causality between AEs and investigational drug

AEs include all unexpected clinical manifestations. All the AEs occurring after the signing of the ICF must be reported in the form of a clinical report according to AE reporting, regardless of whether the AEs are related to the investigational drug, whether the subject is administered with the investigational drug, and whether the subject has been administered with drugs. During the treatment, any discomfort or abnormal changes in objective laboratory tests should be recorded truthfully. The severity, duration, measures taken and outcome of the AE should be indicated. The clinical physician should comprehensively assess the causality between the AE and the study drugs by considering the timing between the administration of study drug and the occurrence of AE, characteristics and toxicology of the study drug, concomitant medications, underlying diseases, medical history, family history, etc. The causality assessment will be provided using the following five categories "definitely related, possibly related, unlikely related, definitely unrelated, and indeterminable".

Related: The AE has a reasonable correlation with the study drug and can be attributed to the study drug from the medical (pharmacological or clinical) point of view.

Unrelated: The AE has no reasonable correlation with the study drug and cannot be attributed to the study drug from the medical (pharmacological or clinical) point of view, and/or there are other reasonable reasons to explain the AE, such as underlying diseases, complications, and concomitant medications.

8.2 Serious Adverse Events (SAEs)

8.2.1 Definition of serious adverse event

A serious adverse event (SAE) refers to a medical occurrence during the clinical study that results in hospitalization, prolonged hospitalization, disability, incapacity, life-threatening or death, or congenital malformation. The following unexpected medical events are included:

- Events resulting in death;
- Life-threatening events (defined as when the subject is at immediate risk of death at the time of the event);
- Events resulting in hospitalization or prolonged hospitalization;
- Events resulting in permanent or serious disability/incapacity/impairment of work ability;
- Congenital anomalies or birth defects;
- Other important medical events (defined as events that may jeopardize the subject or require interventions to prevent any of the above).

8.2.2 Progressive disease and death

Progressive disease (PD) is defined as the deterioration of the subject's conditions caused by the primary tumor targeted by the study drug, including radiological progressions and progressions in clinical symptoms and signs. New metastases relative to the primary tumor or progressions of the previous metastases are recognized as PD. Life-threatening events, hospitalization or prolonged hospitalization, permanent or serious disability/incapacity/impairment of work ability, congenital anomalies or birth defects resulting from signs and symptoms of progressive disease should not be reported as SAEs on an expedited basis. Death caused by the symptoms and signs of PD should be reported as an SAE on an expedited basis.

Death of a subject during the study, regardless of whether a new anti-tumor treatment is administrated, must be reported as an SAE. Deaths caused by symptoms and signs of PD as determined by the investigator shall be recorded in the eCRF and reported as SAEs. The term "death" shall not be used as an AE or SAE, but an outcome of an event. Events that result in death shall be recorded as AEs or SAEs. If the cause of death is unknown and cannot be determined at the time of reporting, the AE or SAE term "death of unknown cause" shall be used for documentation.

8.2.3 Hepatic enzyme abnormalities

If the levels of AST and/or ALT are abnormal and meet the laboratory test abnormalities shown in the table below, such cases of hepatic enzyme abnormalities should be reported as SAEs. The investigator is required to strengthen the follow-up of the subjects, who should be followed up until their hepatic enzyme levels recover to the normal or baseline level.

Baseline Period	Normal (AST/ALT and TBIL)	Abnormal (AST/ALT/TBIL)
Treatment period	ALT or AST $\geq 3 \times \text{ULN}$ with TBIL $\geq 2 \times \text{ULN}$ and ALP $\leq 2 \times \text{ULN}$ and no hemolysis	AST or ALT $\geq 2 \times \text{baseline level}$, and $\geq 3 \times \text{ULN}$ or AST or ALT $\geq 8 \times \text{ULN}$ with increase in TBIL by $\geq 1 \times \text{ULN}$ or TBIL level $\geq 3 \times \text{ULN}$

8.2.4 Other anti-tumor treatments

If the subjects start other anti-tumor treatments, please refer to Section 8.3 for the period of AEs/SAEs reporting. If a death occurs after the end of the study treatment but within the reporting period of serious adverse events, it must be reported promptly regardless of whether the subject received other treatments.

8.2.5 Hospitalization

AEs that result in hospitalization (even if for less than 24 h) or prolonged hospitalization during the clinical study should be considered as SAEs.

Hospitalization does not include the following:

- Hospitalization at a rehabilitation institution
- Hospitalization at a sanatorium
- General emergency admission (less than 24 h)
- Day surgery (e.g., outpatient/same-day/ambulatory surgery)
- For social reasons (medical insurance reimbursement, etc.)

Hospitalization or prolonged hospitalization unrelated to the worsening of an AE is not a SAE.

For example:

- Hospitalization due to the pre-existing disease without new AEs and aggravation of the pre-existing disease (e.g., hospitalization to examine laboratory abnormalities that have persisted before the study until now);
- Hospitalization for management reasons (e.g., annual physical examination);
- Hospitalization during the study as specified in the study protocol (e.g., as required by the protocol);
- Elective hospitalization unrelated to the exacerbation of an AE (e.g., elective cosmetic surgery);
- Scheduled treatment or surgery that should be documented throughout the entire study protocol and/or in the subjects' individual baseline information;
- Hospitalization merely for use of blood products.

Diagnostic or therapeutic invasive (e.g., surgery) or non-invasive procedures should not be reported as AEs. However, the disease condition leading to such procedures should be reported if it meets the definition of an AE. For example, acute appendicitis during the AE reporting period should be reported as an AE, and the resulting appendectomy should be recorded as the treatment of the AE.

8.2.6 Reporting of serious adverse events

In the event of an SAE, whether it is an initial or follow-up report, the investigator must complete the "Serious Adverse Event Report Form" immediately with signature and date, and notify the sponsor within 24 h of awareness. Relevant authorities must be informed of such an SAE in a timely manner according to regulatory requirements.

The symptoms, severity, causality with the study drug, time of onset, time of treatment, measures taken, time and method of follow-up, and outcomes should be documented in detail in the SAE report. If the investigator believes that an SAE is not related to the study drug but potentially related to the study conditions (such as the discontinuation of past treatment, or comorbidities during the study), the causality should be explained in the description section of the SAE report form. If the severity of an ongoing SAE or its relationship to the study drug changes, a follow-up report should be submitted immediately. If an error is found in a previously reported SAE, such SAE may be revised, revoked, or downgraded in follow-up reports and reported in accordance with the SAE reporting procedure.

Email the SAE reports to: [contact]

8.3 Collection and Follow-Up of AEs/SAEs

The collection of AEs/SAEs should start from the time when the subjects sign the informed consent form and end 90 days after the last dose of SHR-1210 or 30 days after the last dose of anti-angiogenic targeted therapy (whichever is longer). SAEs occurring after this period that are suspected to be related to the study drug should be collected. See [Table 8-1](#) below for specific requirements. Any AE/SAE should be followed-up until the event resolves, returns to the baseline level or \leq Grade 1, reaches a steady state, or is reasonably explained (e.g., lost to follow-up, death). The investigator should try to obtain the best outcome and clear causality with the study drug.

During each visit, the investigator should ask about the situation of AEs/SAEs that occur after the last visit and provide follow-up information in a timely manner based on the sponsor's query request.

Table 8-1. Collection period of AEs/SAEs

Classification	Collection/Recording Requirements
AEs Unrelated to the Study Drug	Up to 30 days after the last dose
Treatment-Related AEs ^a	Up to 90 days after the last dose of SHR-1210 or 30 days after the last dose of apatinib (whichever is longer)
SAEs Unrelated to the Study Drug ^a	
 Fatal SAEs: up to 90 days after the last dose of SHR-1210 or 30 days after the last dose of apatinib (whichever is longer) Non-fatal SAEs: up to 30 days after the last dose
Treatment-Related SAEs ^b	No time limit

^a Non-serious AEs

^b Including fatal and non-fatal SAEs.

8.4 Pregnancy

If a female subject becomes pregnant, she must withdraw from the study. The investigator must report to the sponsor within 24 h of being notified of the pregnancy and fill out the "Pregnancy Report/Follow-up Form for Hengrui Clinical Studies". If the partner of a male subject becomes pregnant, the subject may continue the clinical study. The investigator must report to Hengrui within 24 h of being notified of the pregnancy and fill out the "Pregnancy Report/Follow-up Form for Hengrui's Clinical Studies". The investigator should follow up the pregnancy until 1 month after delivery, and report the results to Hengrui.

A negative pregnancy outcome (stillbirth, spontaneous abortion, or congenital malformation) is considered an SAE and should be reported according to the time requirements for SAEs.

If the subject also meets the criteria for an SAE, an SAE report form should be filled out and the SAE should be reported according to the requirements for SAEs as well.

8.5 Adverse Events of Special Interest

When an AE of special interest specified in the study protocol occurs, the investigator must fill out the "Report of Adverse Event of Special Interest for Hengrui Clinical Studies" and report to the sponsor within 24 h of knowing the event. If an AE of special interest is also an SAE, the "NMPA Serious Adverse Event Report Form" must also be completed.

- Grade ≥ 3 infusion reaction
- Grade ≥ 2 diarrhea/colitis, uveitis, interstitial pneumonitis
- Other Grade ≥ 3 immune-related AEs

- Any possible events of hepatic enzyme abnormalities (see 8.2.3, lacking other related causes of the abnormalities at the same time, e.g., PD, acute viral hepatitis, cholestasis, concomitant medication, concurrent liver disease, etc.)
- Grade 4 amylase or lipase increased

8.6 Infusion Reactions

During the course of this study, the investigator should pay close attention to potential infusion and/or allergic reactions, especially acute immune-mediated adverse reactions (including cytokine storms).

Generally, there is no need for prophylactics before infusion of SHR-1210. Based on published relevant information, an allergic reaction/event is most likely to occur within 24 h after infusion. If an allergic reaction/event occurs, the infusion should be slowed or interrupted according to the situation, and a supportive treatment should be given. In addition, prophylactics should be given before further administration. Possible allergic reactions include fever, chills, shiver, headache, rash, pruritus, joint pain, hypotension/hypertension, or bronchospasm. All Grade 3 or 4 infusion reactions should be reported in accordance with SAE reporting procedures.

8.7 Immune-Related Adverse Events (irAEs)

Immune-related adverse events (irAEs) are clinically significant side effects that are consistent with the immunological mechanisms of the study drug. irAEs require further serological, immunological and pathological (biopsy) data to support its diagnosis. Also, tumors, infections, metabolism, toxins, or other pathogenic factors must be ruled out.

Management principles for immune-related adverse events (see Appendix IV for details):

● Immune-related pneumonitis

In the clinical study of SHR-1210, the monitoring of signs and symptoms of immune-related pneumonia, such as cough and chest discomfort, in the subjects will be strengthened. Examinations will be carried out via imaging tests (e.g., X-ray), and a high-dose hormone therapy will be given to subjects with a Grade 2 or greater event. Subjects with a Grade 2 event can interrupt SHR-1210 and be treated, but subjects with a Grade 3 or 4 event should permanently discontinue SHR-1210.

- **Immune-related enteritis**

In the clinical study of SHR-1210, the monitoring of signs and symptoms of immune-related enteritis, such as abdominal pain, diarrhea, and hematochezia, in the subjects will be strengthened. A high-dose hormone therapy will be given to subjects with a Grade 2 or greater event. Subjects with a Grade 2 or 3 event can interrupt SHR-1210 and be treated, but subjects with a Grade 4 event should permanently discontinue SHR-1210.

- **Immune-related hepatitis**

In the clinical study of SHR-1210, the monitoring of signs and symptoms of immune-related hepatitis, such as liver discomfort and abnormally increased transaminase, in the subjects will be strengthened. A high-dose hormone therapy will be given to subjects with a Grade 2 or greater event. Subjects with a Grade 2 event can interrupt SHR-1210 and be treated, but subjects with a Grade 3 or 4 event should permanently discontinue SHR-1210.

- **Immune-related thyroid dysfunction**

Thyroid dysfunction can occur at any time during the study. Therefore, in clinical studies of SHR-1210, thyroid functions of subjects will be regularly examined to closely monitor the clinical symptoms of thyroid dysfunction. After the occurrence of immune-related hyperthyroidism, the subject should be given a high dose of cortisone/prednisone. Hormone replacement therapy is used for the treatment of hypothyroidism, but glucocorticoids are not applicable.

In the clinical study of SHR-1210, the monitoring of signs and symptoms of immune-related thyroid dysfunction in the subjects will be strengthened. A high-dose hormone therapy will be given to subjects with a Grade 3 or greater event, but subjects with a Grade 4 event should permanently discontinue SHR-1210.

- **Immune-related nephritis and renal failure**

In the clinical study of SHR-1210, the monitoring of signs and symptoms of immune-related nephritis in the subjects will be strengthened. A high-dose hormone therapy will be given to subjects with a Grade 2 or greater event. Subjects with a Grade 2 event can interrupt SHR-1210 and be treated, but subjects with a Grade 3 or 4 event should permanently discontinue SHR-1210.

● Immune-related hypophysitis

In the clinical study of SHR-1210, the monitoring of signs and symptoms of immune-related hypophysitis in the subjects will be strengthened. A high-dose hormone therapy will be given to subjects with a Grade 2 or greater event. Subjects with a Grade 2 or 3 event can interrupt SHR-1210 and be treated, but subjects with a Grade 4 event should permanently discontinue SHR-1210.

● Other immune-related adverse reactions

In principle, interruption of SHR-1210 is preferred based on the severity of the adverse reaction. The study treatment can be considered to resume when AE returns to Grade ≤ 1 . The study treatment should be permanently discontinued if severe (Grade 3) or life-threatening (Grade 4) adverse reactions occur.

The treatment of immune-related adverse reactions should be based on the medical practice and guidelines of the study center. The treatment recommendations for irAEs are shown in Table 8-2 for reference.

Table 8-2. Treatment recommendations for irAEs related to SHR-1210 for injection

CTCAE Grade	Clinical Management*	SHR-1210 Treatment
Grade 1 (mild)	
 - Close observation, especially for diarrhea • Supportive care 	Continue
Grade 2 (moderate)	
 - Closely monitoring • Supportive care • Local application of steroids, such as for dermatitis/colitis, etc. 
Symptoms persist for ≥ 7 days, start 1 mg/kg of prednisone or equivalent
 
Symptoms are aggravated, give intravenous or oral administration of 1 mg/kg prednisone
	Interrupt, resume when recovers to Grade ≤ 1
Grade ≥ 3 (severe)*	-2 mg/kg of prednisone or equivalent	Permanent discontinuation

* The treatment may not be interrupted for Grade 3 local skin and endocrine disorders, because they can often heal (skin) or be treated using an alternative treatment (endocrine)

(Weber, [name], et al., "Toxicities of immunotherapy for the practitioner," J Clin Oncol, April 2015)

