6.4 Dose Modification

The study treatment may be modified according to the toxic side effects appeared. The options for treatment modification include: interruption, dose reduction, change in method of administration, and discontinuation;

In this study, only interruptions for up to 12 weeks are permitted for SHR-1210 treatment; A SHR-1210 dose delayed by more than 3 days shall be skipped, and the administration may be resumed at 200 mg at the next scheduled time point.

Dose modifications caused by apatinib-related toxicity include: dose interruption, dose reduction (500 mg/d or 375 mg/d dose groups), change in method of administration (first modification: 5 days of drug administration followed by 2 days of dose interruption; re-modification: 1 day of drug administration followed by 1 day of dose interruption), and discontinuation. Further adjustments will not be allowed after the dose or method of administration of apatinib is modified during the study period, unless such adjustments are agreed upon by the investigator and the sponsor after discussion.

In the event of an apatinib-related adverse reaction, the dose should be interrupted first. After the toxicity has returned to an acceptable level, the following options may be selected as appropriate: resume administration using the original dose, reduce the dose, modify the method of administration or discontinue the drug. Subjects may continue SHR-1210 as monotherapy if apatinib treatment is discontinued.

For immune-related toxicity occurring during the study, such as immune-related pneumonitis, hepatitis and colitis, the administration of SHR-1210 and apatinib should be interrupted as appropriate. The administration can be resumed when the toxicity returns to Grade ≤ 1 or baseline levels (for subjects with abnormal laboratory parameters such as ALT/AST and TBIL at baseline). The administration of SHR-1210 should be resumed first. The administration of apatinib can be resumed when no significant abnormality is observed within 7 to 14 days after SHR-1210 administration. The route of subsequent administration of apatinib should be modified.

Rules for Dose Modifications

Treatment-Related Toxicity		Grade	Whether to Interrupt Treatment		Criteria for Resuming	Dose Modification Method	Criteria for Discontinuation
			SHR-1210	Apatinib			
Toxicity related to SHR-1210 and apatinib	Hematologic toxicity (except for decreased lymphocyte count)	Grade 1-2	No	No	—	—	—

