		Grade 3	No	Yes	Until the toxicity returns to Grade ≤ 2	Resume at original dose	Two episodes of Grade 4 hematological toxicity
		Grade 4	Yes	Yes	Until the toxicity returns to Grade ≤ 2	Dose reduction or modification of method of administration	
	Non-hematologic toxicity	Grade 1	No	No	—	—	—
		Grade 2 (last for ≥ 7 d)	Yes	Yes	Until the toxicity returns to Grade ≤ 1	Resume at original dose	SHR-1210 interruption for more than 12 weeks
		Grade 3	Yes	Yes	Until the toxicity returns to Grade ≤ 1	Dose reduction or modification of method of administration	
Toxicity related to SHR-1210	Reactive capillary endothelial proliferation	Grade 3	Yes	No	Until the toxicity returns to Grade ≤ 2	Resume at original dose	SHR-1210 interruption for more than 12 weeks

Treatment-Related Toxicity		Grade	Whether to Interrupt Treatment		Criteria for Resuming	Dose Modification Method	Criteria for Discontinuation
			SHR-1210	Apatinib			
Apatinib-Related Toxicities	Hypertension	Grade 3 (after corrective treatment)	No	Yes	Wait until blood pressure returns to within 140/90 mmHg	Dose reduction or modification of method of administration	Subjects with persistent Grade 3 hypertension after the best corrective treatment and the modification of method of administration of apatinib
	Proteinuria (without significant increase in blood creatinine)	Grade 3 (24 h urine protein quantification)	No	Yes	Until the toxicity returns to Grade ≤ 2	Dose reduction or modification of method of administration	Subjects with persistent Grade 3 proteinuria after the best corrective treatment and the modification of method of administration of apatinib
	Hand-and-foot syndrome	Grade 3	No	Yes	Until the toxicity returns to Grade ≤ 1	Dose reduction or modification of method of administration	Subjects with persistent Grade 3 hand-and-foot syndrome after the best corrective treatment and the modification of method of administration of apatinib
	Headache	Grade 2 (last for ≥ 7 d) or Grade 3	No	Yes	Until the toxicity returns to Grade ≤ 1	Dose reduction or modification of method of administration	Apatinib interruption for more than 28 days

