During the study, in the case of Grade ≥ 3 immune-related pneumonitis, Grade ≥ 3 TBIL elevation (recurrent), Grade 4 ALT/AST elevation (recurrent), other Grade 4 immune-related toxicities (except for hypothyroidism), Grade 4 injection reactions, or the interruption of SHR-1210 administration for more than 12 weeks due to immune-related toxicity but the toxicity is still unable to return to Grade ≤ 1 or baseline levels (subjects with baseline abnormality), SHR-1210 should be permanently discontinued.

After discontinuation of SHR-1210 treatment, subjects may continue to receive apatinib monotherapy after toxicity recovery if the investigator judges that the subjects can benefit from the apatinib monotherapy, until an event meeting the criteria for discontinuation as specified in the protocol occurs.

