Appendix IV Management Principles for irAEs

1. Management Principles for Gastrointestinal AEs

[figure not shown]
Non-inflammatory causes of disease should be excluded. Opioids/anesthetics may mask the symptoms of perforation. Do not use infliximab in the case of perforation/sepsis.

If subjects receiving intravenous injection of steroids show continuous clinical improvements, it is allowed, at the start of dose tapering or earlier, to switch to oral administration of corticosteroids (such as prednisone) at equivalent dose. When switching to oral corticosteroids with an equivalent dose, it should be considered that the bioavailability of oral corticosteroids is relatively low.

2. Management Principles for Pulmonary AEs

[figure not shown]
Non-inflammatory causes of disease should be excluded. If it is due to a non-inflammatory cause, a symptomatic treatment should be given while the I-O therapy should be continued. Imaging evaluation and consultations with the respiratory department should be performed.

If subjects receiving intravenous injection of steroids show continuous clinical improvements, it is allowed, at the start of dose tapering or earlier, to switch to oral administration of corticosteroids (such as prednisone) at equivalent dose. When switching to oral corticosteroids with an equivalent dose, it should be considered that the bioavailability of oral corticosteroids is relatively low.

3. Management Principles for Hepatic Adverse Events

Non-inflammatory causes of disease should be excluded. If it is due to a non-inflammatory cause, a symptomatic treatment should be given while the I-O therapy should be continued. Consider imaging examinations to rule out obstruction/tumor progression.

[figure not shown]
If subjects receiving intravenous injection of steroids show continuous clinical improvements, it is allowed, at the start of dose tapering or earlier, to switch to oral administration of corticosteroids (such as prednisone) at equivalent dose. When switching to oral corticosteroids with an equivalent dose, it should be considered that the bioavailability of oral corticosteroids is relatively low.

* If AST/ALT $\leq 8 \times$ ULN and T. Bili $\leq 5 \times$ ULN, I-O treatment can be delayed rather than discontinued.

**For Grade 4 hepatitis, the recommended starting dose of methylprednisolone intravenous injection is 2 mg/kg/day.

[figure not shown]
4. Management Principles for Endocrine Adverse Events

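### For a first Grade 3 immune-related nephritis or residual 'other' irAE (local skin and endocrine disorders apart), Protocol 8.7 and 9.1 stop treatment permanently while 6.4 lets it resume; Grade 3 hepatitis has no consistent instruction, and nothing visible says which text prevails

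*Protocol*

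**What the plan says.** Protocol 8.7 sets a stop by organ. In both the nephritis and the hepatitis bullets, "subjects with a Grade 3 or 4 event should permanently discontinue SHR-1210". For immune-related reactions not named individually, "The study treatment should be permanently discontinued if severe (Grade 3) or life-threatening (Grade 4) adverse reactions occur". Table 8-2, which is offered for reference, also gives permanent discontinuation at Grade 3 or above, with a footnote: "The treatment may not be interrupted for Grade 3 local skin and endocrine disorders". The reason given there is that such events often heal or can be managed otherwise, so I read it as 'need not be interrupted'.

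Protocol 9.1 repeats the Grade 3 stop for nephritis and for the residual category. Its hepatitis bullet gives steroid doses for Grades 2 and 3 and says nothing about stopping SHR-1210.

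Protocol 6.4 has its own immune-toxicity paragraph. For events "such as immune-related pneumonitis, hepatitis and colitis, the administration of SHR-1210 and apatinib should be interrupted as appropriate". Then: "The administration can be resumed when the toxicity returns to Grade ≤ 1 or baseline levels". It also gives an order for restarting: SHR-1210 first, and apatinib if nothing significant appears within 7 to 14 days. In the dose-modification table, Grade 3 non-hematologic toxicity also resumes at Grade 1 or below, and the discontinuation criterion shown for that block is "SHR-1210 interruption for more than 12 weeks". The list of permanent stops later in 6.4 has Grade 3 or above for pneumonitis, and then "Grade ≥ 3 TBIL elevation (recurrent), Grade 4 ALT/AST elevation (recurrent), other Grade 4 immune-related toxicities (except for hypothyroidism", plus Grade 4 injection reactions and immune toxicity that has not recovered after more than 12 weeks' interruption.

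Appendix IV adds a hepatic footnote: if AST/ALT is at most 8 × ULN and total bilirubin at most 5 × ULN, "I-O treatment can be delayed rather than discontinued".

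**The concern.** The decision at issue is whether a patient who has recovered from a severe immune-related organ toxicity is given the PD-1 antibody again. A site working from the dose-modification section would conclude that it may restart. A site working from the immune-event section would conclude that it must not. Both would be following the protocol.

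The main stake is patient safety. There is a smaller reporting consequence. SAP 5.4.3 tabulates adverse events leading to discontinuation of SHR-1210 separately from those leading to interruption, so the same clinical event can fall in either table. A restart departs from 8.7 but not from 6.4, so its classification as a protocol deviation (SAP 5.2.7), and possibly membership of the per-protocol set (SAP 5.1.1), could turn on which section is applied.

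**Working it through.** No arithmetic decides this. The check sets out the rule for a first Grade 3 event in each place.

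| Event, Grade 3 | 8.7 organ text | 9.1 | 6.4 | Result |
|---|---|---|---|---|
| Pneumonitis | stop | stop | stop (listed at Grade 3 and above) | agree |
| Enteritis | interrupt | interrupt | may resume; stop at Grade 4 | agree |
| Hypophysitis | interrupt | interrupt | may resume; stop at Grade 4 | agree |
| Thyroid dysfunction | no stop | no stop | may resume | no conflict |
| Nephritis | stop | stop | may resume; stop at Grade 4 | conflict |
| Residual irAEs | stop study treatment | stop study treatment | may resume; stop at Grade 4 | conflict, except local skin and endocrine |
| Hepatitis | stop | steroid dosing, no stop | named as resumable; only recurrent elevations listed | inconsistent; Appendix IV adds a conditional delay |

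**Nephritis and the residual category.** The 6.4 list assigns immune-related toxicities it does not name to Grade 4. Sections 8.7 and 9.1 assign these events to Grade 3. These are two stated thresholds for one decision, so the conflict does not rest on silence.

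**Hepatitis.** Four places speak to it: 8.7 stops, 6.4 names it in the interrupt-and-resume sentence and lists only recurrent liver elevations, 9.1 gives no stop, and Appendix IV allows delay within limits. The Appendix IV flowchart is not shown, so how its footnote fits with the 8.7 stop cannot be checked.

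**Precedence.** Sections 8.7 and 9.1 both say that treatment of these reactions follows the study center's practice and guidelines. That concerns how the reaction is treated; it does not say whether 6.4 or 8.7 governs restarting SHR-1210. The words 'for reference' attach to Table 8-2 in 8.7 and to Appendix IV in 9.1. The 8.7 organ bullets carry no such label. No visible text has one section defer to the other on this decision.

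**How many subjects.** The nearest figure is in Section 1.7.1: 2.3% Grade 3 or greater treatment-related AEs in the Chinese phase I studies. With 87 subjects that is 0.023 × 87 ≈ 2 people, across all organs and several tumour types, on SHR-1210 without apatinib. It cannot support an estimate for these organs under the combination.

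**The case against.** The strongest reply is that 6.4 governs. It presents its content as rules for dose modification, whereas 8.7 calls its bullets management principles and 9.1 introduces its own as recommendations. That is fair evidence of relative status, but it is not a precedence clause, and the 8.7 bullets still say that subjects should permanently discontinue.

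A second reply is that the resume sentence in 6.4 is not an unlimited permission. It names pneumonitis as well, yet 6.4 itself stops pneumonitis at Grade 3. This is correct: the stop list evidently limits the resume sentence. The question then becomes what the list covers, and for nephritis and the residual category it gives Grade 4. For hepatitis the argument has more force, because a first Grade 3 event is simply absent and the list does not claim to be exhaustive. The 12-week criterion in the table is also less certain support, since applying it to the Grade 3 row assumes a merged cell in a table that was read by program.

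A third reply is that 6.4 only permits resumption, so stopping satisfies every section. That is true, but only a site that consults 8.7 would know that stopping is called for.

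Stronger readings are tempting, and the documents do not support them:

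- **Every Grade 3 irAE is in conflict.** Pneumonitis, enteritis and hypophysitis agree, thyroid dysfunction shows no conflict, and Table 8-2 exempts local skin and endocrine disorders.
- **Grade 3 hepatitis is a clean contradiction.** The Appendix IV delay softens the 8.7 stop for some cases.
- **The sections also disagree at Grade 4.** A diagnosed first Grade 4 hepatitis can be read into the 6.4 entry for remaining Grade 4 immune toxicities. The 8.7 thyroid stop sits in a sentence about high-dose hormone therapy, while 8.7 says glucocorticoids do not apply to hypothyroidism. It can therefore be read as hyperthyroidism, in line with the 6.4 exemption.

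**Conclusion.** The concern holds in a limited form. The discontinuation rule for a first Grade 3 event is contradictory for immune-related nephritis and for residual irAEs other than local skin and endocrine disorders. For Grade 3 hepatitis it is inconsistent across 6.4, 8.7, 9.1 and Appendix IV. Re-exposure after such an event depends on which text the site reads.

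The size is modest. I expect few subjects to be affected, and the documents give no usable rate. A reader might infer that the primary endpoint is threatened; the documents do not support that. SAP 4.1.1 counts response up to progression or new anti-tumour treatment, so stopping SHR-1210 does not by itself end the assessment window, and 6.4 allows apatinib to continue alone. The effect on ORR should be small. This is a safety-conduct point that should be corrected.

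The conclusion assumes that the Appendix IV flowcharts, which are not shown, contain no ranking of the sections, and that the Table 8-2 footnote means interruption is not required.

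**What to change.** Make the permanent-discontinuation list in 6.4 the single rule, using thresholds the protocol already contains.

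1. **Grade 3 or above:** permanently discontinue SHR-1210 for immune-related pneumonitis, hepatitis, nephritis and irAEs not otherwise named, except Grade 3 local skin and endocrine disorders.
2. **Grade 4:** permanently discontinue for enteritis, hypophysitis and thyroid dysfunction other than hypothyroidism. Keep the existing 12-week non-recovery rule.
3. **Resume text:** make both the resume sentence in the 6.4 immune-toxicity paragraph and the Grade 3 non-hematologic row of its table subject to that list. Changing the list alone would leave the conflict inside 6.4.
4. **Endocrine events:** leave Grade 3 thyroid and other endocrine events under the Table 8-2 footnote, with no mandatory interruption.
5. **Residual irAEs:** state whether the stop applies to SHR-1210 only or to all study treatment. The present 8.7 wording covers study treatment, whereas its nephritis and hepatitis bullets name SHR-1210.
6. **Cross-references:** have 8.7, Table 8-2 and 9.1, including its hepatitis bullet, point to the list.
7. **Liver exception:** if the Appendix IV delay is intended, write AST/ALT ≤ 8 × ULN and total bilirubin ≤ 5 × ULN into the list as the only liver exception.

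The cost is amendment wording and site notification, with no change to sample size or visits. A few subjects with recovered Grade 3 events would lose the option to resume SHR-1210.
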